2. DESIGN AND METHOD

2.1 Study Site:

Study will be conducted University of Peradeniya.

2.2 Study Population:

Undergraduates who are currently having upper back pain for more than seven days will be selected as sample. Participants who will have sub-acute and chronic pain which means who will have pain more than a week or seven days will be selected as sample and who have subjected to any recent surgeries, recent fractures, accidents or injuries in upper back will be excluded from the study.

2.3 Study Setting:

Study will be conducted in Service unit of Department of physiotherapy at University of Peradeniya.

2.4 Study Design:

This study is a Randomized Control Trial, Double- Blinded study. Participants and assessors will be blinded. Participants will be allocated randomly in to two groups which are experimental group which will receive thoracic mobility exercises and control group which will receive myofascial release and joint mobilization treatment.

2.5 Hypothesis:

1. Hypothesis about difference in baseline characteristics of participants between control and experimental groups

Null Hypothesis: $H_0: \mu_1 - \mu_2 = 0$

There is no difference in baseline characteristics of participants between experimental and control group.

Alternate Hypothesis: $H_1: \mu_1 - \mu_2 \neq 0$

There is a difference in baseline characteristics of participants between experimental and control group

2. Hypothesis about differences in pain intensity between control group and experimental group.

Null Hypothesis: $H_0: \mu_1 - \mu_2 = 0$

There is no difference in pain intensity of participants between experimental and control group.

Alternate Hypothesis: $H_1: \mu_1 - \mu_2 \neq 0$

There is a difference in pain intensity of participants between experimental and control group

3. Hypothesis about differences in thoracic mobility (Range of Motion) between control group and experimental group.

Null Hypothesis: $H_0: \mu_1 - \mu_2 = 0$

There is no difference in thoracic mobility of participants between experimental and control group.

Alternate Hypothesis: $H_1: \mu_1 - \mu_2 \neq 0$

There is a difference in thoracic mobility of participants between experimental and control group

4. Hypothesis about differences in muscle strength of spinal extensors between control group and experimental group.

Null Hypothesis: $H_0: \mu_1 - \mu_2 = 0$

There is no difference muscle strength of spinal extensors of participants between experimental and control group.

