Alternate Hypothesis: $H_1: \mu_1 - \mu_2 \neq 0$

There is a difference in muscle strength of spinal extensors of participants between experimental and control group

5. Hypothesis about differences in disability of participants between control group and experimental group.

Null Hypothesis: $H_0: \mu_1 - \mu_2 = 0$

There is no difference in disability of participants between experimental and control group.

Alternate Hypothesis: $H1: \mu_1 - \mu_2 \neq 0$

There is a difference in disability of participants between experimental and control group.

2.6 Sample Size:

Sample size is Calculated by using G*power 3.1.9.4 software by assigning power 80% effective size 0.5, type I error = 0.05 and type II error = 0.2. Therefore calculated sample size was 42. Drop down rate of participants is assigned as 25 %. Therefore final sample size which obtained is 60 (Kang, 2021).

2.7 Sampling method:

Simple Random Sampling will be used as sampling technique as well as 30 Participants will be randomly allocated to each group. Participant will be allocated to the groups by using lottery method.

2.8 Data collection:

Undergraduates who are having upper back pain more than 7 days will be selected as sample and those who are having any contraindications, recent surgeries, fractures, accidents will be excluded from the students. Informed consent will be obtained from the participants. Participants will be allocated to one group by blindly select the number by lottery method. Thirty participants will be allocated randomly to each group. Allocation was concealed. Assessors will not be aware of intervention or control group and collect the demographic data, Pain assessment, Range of Motion and muscle strength at the baseline and after two weeks of intervention.

2.9 Data collection tool:

Measurement tool contains two sections such as pre-test and post-test questionnaire. In Pre-test questionnaire, there are six sections which includes personal details of the participants, pain related questions, Measurement of range of motion at base line, muscle strength at base line and pain-self-efficacy Questionnaire (PSEQ) at base line. In Post-test questionnaire, there are 4 sections which include, pain related questions

mainly pain intensity after two weeks, muscle strength after two weeks, Range of motion after two weeks and pain-self-efficacy Questionnaire (PSEQ).

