Personal details of the participants will be collected separately for the concealed allocation and participants will be identified by code number. Participants' age, gender, height, weight, BMI, family size, bread winner of the family, monthly income and financial support for the study will be collected in the demographic data section. In third section, questions related to occurrence of pain, pain duration and treatments which were undertaken for the pain will be collected from the participants.

VAS scale will be used to measure the intensity of pain in different situations which include present pain intensity, in sitting, in forward bending, in standing, in walking, in sleeping, in transferring and during day to day activities. Visual Analogue Scale will be used to measure the pain intensity. Subjects will be asked to mark the number between 0 and 10 that fits best to their pain intensity. Zero indicates 'no pain at all' whereas 10 represents 'the worst pain ever possible' (Figure 1). Measurement will be obtained in the baseline and at the end of two weeks.

[figure not shown]

Figure 1- VAS Scale

Thoraco-Lumbar flexion and Extension of thoracic spine Range of Motion will be taken in the fourth section. Measurement will be taken by using measuring tape. Measurement will be taken at the baseline and after two weeks. In the fourth section, muscle strength of thoracic spine extensors will be measured using Oxford-Grading Scale. Measurement will be taken at the baseline and after two weeks. The Oxford Muscle Scale is a numerical rating scale used to quantify the power or strength produced by the contraction of a muscle. The scale was originally developed by a UK government research group called the Medical Research Council (MRC). Reliability of the scale

explained by Intraclass Correlation Coefficient (ICC) and Interrator Reliability. It shows high ICC coefficient of 0.95 (ranging from 0.92 to 0.97) (Hermans et al., 2012).

Muscle Strength Grading Scale (Oxford Scale)	
0/5	No Contraction
1/5	Visible/palpable muscle contraction but no movement
2/5	Movement with gravity eliminated
3/5	Movement against gravity only
4/5	Movement against gravity with some resistance
5/5	Movement against gravity with full resistance

Table 1

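### Entry is set by pain duration alone, with no minimum pain score, so low scorers can enter with little or no room to improve and may dilute the pain comparison by an amount the documents cannot fix

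*Combined protocol and SAP*

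**What the plan says.** Section 2.2 defines the population as follows: "Undergraduates who are currently having upper back pain for more than seven days will be selected as sample". Section 2.8 restates it: "Undergraduates who are having upper back pain more than 7 days will be selected as sample". The exclusions in section 2.8 concern safety and recent trauma: "those who are having any contraindications, recent surgeries, fractures, accidents will be excluded from the students". Section 2.2 excludes recent surgery, fracture, accident or injury of the upper back. Neither section mentions intensity, and neither do the outcome list in section 2.11 or the pre-test form in Annex II.

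Pain is scored under section 2.9: "Subjects will be asked to mark the number between 0 and 10 that fits best to their pain intensity". There are eight separate ratings: "present pain intensity, in sitting, in forward bending, in standing, in walking, in sleeping, in transferring and during day to day activities". Hypothesis 2 in section 2.5 is two-sided ("There is a difference in pain intensity of participants between experimental and control group") and does not say which rating it concerns. Section 2.12 compares the arms after treatment with a two-sample t test and mentions no baseline adjustment. Section 2.6 sizes the trial "by assigning power 80% effective size 0.5, type I error = 0.05 and type II error = 0.2" and ties that effect size to no baseline pain level.

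**The concern.** Section 1.1 links this population's pain to long sitting and screen use, so pain is likely to depend on the situation. A student can truthfully have had upper back pain for more than a week and still give 0 or 1 for present pain, walking or sleeping at the assessment. On a scale bounded at 0, that participant can show little or no benefit in either arm. The more such entrants there are, the smaller the observable difference between treatments. A null result on hypothesis 2 could then reflect a floor in the scale rather than equivalence of the treatments. The concern is confined to the pain items. It does not by itself reach range of motion, muscle strength or the self-efficacy score.

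**Working it through.** **The plan's own figure.** At a standardised difference of d = 0.5, two-sided alpha 0.05 and 80% power, a two-sample t test needs 64 per arm (128 in total), so the stated 42 is not reproduced. Power at d = 0.5 is 35% with 21 per arm and 48% with 30 per arm. That shortfall is a separate matter, but it leaves no slack to absorb dilution.

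**Simple dilution.** Let a share q of entrants contribute no between-arm difference, with the SD unchanged: d = 0.5 × (1 − q). The values of q are assumptions.

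| q | d | power, 21 per arm | power, 30 per arm |
|---|---|---|---|
| 0% | 0.50 | 35% | 48% |
| 20% | 0.40 | 24% | 33% |
| 40% | 0.30 | 16% | 21% |

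**Simulation with a floor.** None of these inputs is in the documents except the 0-10 scale, 30 per arm and the t test.
- Baseline is normal with mean μ and SD 2, rounded and clipped to 0-10.
- The two-week score is the treated value plus a residual with SD 1.2, rounded and clipped.
- Proportional effect: baseline × 0.7 in one arm and × 0.5 in the other.
- Constant effect: baseline − 1.0 and baseline − 1.8.
- Sixty are enrolled in every case. There were 100,000 trials per cell.

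The share screened out by a minimum of 3 is Φ((2.5 − μ)/2). The number to screen for 60 entrants is 60/(1 − share).

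| μ | screened out | to screen | proportional: no minimum → at least 3 | gain | constant: no minimum → at least 3 | gain |
|---|---|---|---|---|---|---|
| 2 | 60% | 150 | 19% → 57% | 39 | 22% → 44% | 23 |
| 3 | 40% | 100 | 30% → 62% | 32 | 23% → 39% | 16 |
| 4 | 23% | 78 | 44% → 66% | 22 | 24% → 35% | 11 |
| 5 | 11% | 67 | 61% → 74% | 13 | 25% → 31% | 6 |
| 6 | 4% | 63 | 76% → 81% | 6 | 25% → 28% | 3 |

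Gains are in percentage points, taken before rounding. Smaller runs gave 7 to 39 and 2 to 24, the same within simulation error. A larger constant effect (falls of 1 and 2 points) gives gains of 31 points at μ = 2 and 4 at μ = 6.

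**Zeros removed.** If the current-pain requirement keeps out every 0, the comparison is entry at 1 or more against 3 or more. For the proportional effect this is 29% → 57% at μ = 2, 38% → 62% at μ = 3 and 49% → 66% at μ = 4.

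**Where the gain comes from.** With the constant effect at μ = 4, the expected difference rises from 0.69 to 0.78 points and the SD falls from 2.09 to 1.91. So d goes from 0.69/2.09 = 0.33 to 0.78/1.91 = 0.41. The larger difference alone would give 0.78/2.09 = 0.37. About half the gain is a narrower baseline spread, not relief from the floor.

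**Baseline adjustment with no minimum** (4,000 trials per cell).

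| μ | proportional | constant |
|---|---|---|
| 2 | 29% | 48% |
| 3 | 49% | 56% |
| 4 | 70% | 61% |

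For the constant effect, adjustment alone beats the threshold alone at each of these means. For the proportional effect it does so at μ = 4 (70% against 66%) but not at 2 or 3. Doing both gives 67%, 75% and 83% for the proportional effect. These figures rest on a high correlation between baseline and follow-up: ignoring clipping, 1.4/√(1.4² + 1.2²) = 0.76 in the × 0.7 arm. A weaker correlation would reduce what adjustment recovers.

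**The case against.** A reader might infer that anyone scoring 0 to 2 cannot improve. That holds only at 0: a 1 can fall by one point and a 2 by two. Section 2.2 also requires current pain, so a 0 should arise only on a single situational item or with intermittent pain. This part of the objection stands, and it lowers the estimated gain without removing it.

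A reader might also infer that the trial has lost a known and large amount of power. The documents give no baseline mean, SD or share of low scorers, and no form for the treatment effect. If typical baseline pain is 5 or 6, the floor matters little. Much of the loss at low means can be recovered by adjusting for baseline, which excludes nobody. These points stand too.

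Finally, it is tempting to call screening nearly free because section 1.1 cites upper back pain in 46.9% of an undergraduate sample. That figure is a prevalence among dental students in Saudi Arabia and says nothing about intensity. The gain and the screening burden rise together: where the threshold helps most, 40% to 60% of candidates would be turned away within the three months of data collection in section 2.13. If 60 could not then be enrolled, part of the gain would be lost.

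Admitting pain of any severity is a legitimate choice of population, and the other hypotheses do not need a pain threshold. The plan does not, however, state or defend that choice for hypothesis 2.

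**Conclusion.** The point holds as a design improvement. The documents set no minimum pain score, the pain scale has a floor at 0, and the planned comparison is unadjusted, so low scorers can enter and can weaken the test of hypothesis 2. The direction was the same in every setting checked. The size is not established: about 6 to 39 percentage points of power for a proportional effect and about 3 to 23 for the constant effect of 1.0 against 1.8 points, at 30 per arm with 60 enrolled. Both ranges rest on assumed means of 2 to 6, baseline SD 2 and residual SD 1.2. They are scenarios, not forecasts. The documents do not show that many participants will be at the floor, or that a null result is likely for this reason.

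**What to change.** Make three linked changes.
1. In sections 2.5 and 2.11, name one of the eight existing VAS items as the rating for hypothesis 2. Without this, a threshold has nothing to attach to.
2. In sections 2.2 and 2.8, add a prespecified minimum on that item, recorded before the lot is drawn. At least 3 out of 10 is an example only; the documents support no particular cut-off, and the investigators should justify theirs.
3. In section 2.12, adjust the two-week pain comparison for the baseline score, for example by ANCOVA.

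The form already collects the ratings, so no new measurement is needed. The cost is screening: about 63 to 150 volunteers for 60 entrants over the assumed range, and a result that applies only to participants at or above the threshold. If the investigators prefer to keep all severities, the first and third changes still recover part of the lost power, and the plan should say that the choice is deliberate. The sample size should then be based on the difference and SD expected in the population chosen.

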5.3 Annex III: Treatment Protocol

Experimental Group:

Thoracic Mobility exercises

1. Cat and Camel exercise:

Subject has to position himself on their hands and knees on the floor. Head has to be in relaxed position and allowed to drop down (figure 5.3.1). First, Subject has to round his back toward the ceiling until he or she feel a nice stretch in his or her upper and middle back. When Perform this technique subject has to inhale (figure 5.3.2). Hold this stretch for 10 seconds. Then subject has to return to the starting position with flat back. While doing this subject has to exhale. Subject has to let his back sway by pressing his or stomach toward the floor (Figure 5.3.3). Hold this Position for 10 seconds. Repeat for 5 times.

Figure 5.3.1

Figure 5.3.2

Figure 5.3.3

2. Horizontal Chest Expansion:

Subject has to stand shoulder width apart. Bring the hands in front of the body to the shoulder level and palm of each hand to be touched each other (parallel to the floor)(figure 5.3.4). While breathing in or inhaling bring both hands apart from each other to the side and go beyond the side of the body (Figure 5.3.5). After that, This Position has to hold for 10 seconds. Then, while exhaling hands have to return back to the normal position. Exercise has to repeat for 5 times.

Figure 5.3.4

Figure 5.3.5

3. Cross arm chest expansion:

Subject has to stand shoulder width apart. Subject has to gently cross arms, so that finger tips point to the opposite shoulder. Then, Subject has to keep the lower body stable and turn the upper body from side to side allowing with head to follow the movement. Subject has to keep the movement controlled and smooth (figure 5.3.6). Repeat 5 times.

Figure 5.3.6

Subjects has to perform these exercise two times a day. Exercise has to be performed with 5 minutes break for up to two weeks. Participants to be examined 3 times in a week whether they performed correctly.

Control Group:

Myofascial release:

Participants will be properly placed in prone lying position and adequate Therapist will palpate the muscle (spinal extensors) and trigger points will be identified. Constant pressure will be applied for 90 seconds to release the painful points as illustrated in Figure 5.3.7

Figure 5.3.7

Thoracic Spine Mobilization (Maitland technique):

Postero-anterior central vertebral pressure:

Starting position:

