Subject will be positioned in prone with forehead relaxed in the back of the hands. For mobilizing upper thoracic spine (T1-T5). Therapist positioned himself to the right angle to the mobilizing surface area of the body. The pads of the thumbs are placed on the spinous process, pointing transversely across the vertebral column, and the fingers of each hand are spread out over the posterior chest wall to give stability to the thumbs. The pressure should be transmitted through the thumbs so that the interphalangeal joints are hyperextended with a slight degree of Flexion in the metacarpophalangeal joints (as illustrated in figure 5.3.8 - C).

To mobilize the mid-thoracic spine (T5–9), the physiotherapist should stand at the patient's side at the waist level with her thumbs placed longitudinally along the vertebral column so that they point towards each other. The fingers can then spread out over the posterior chest wall, to each side of the vertebral column above and below the thumbs (as illustrated in Figure 5.3.8 -A).

For the lower thoracic spine (T10–12), the physiotherapist's position depends upon the shape of the patient's chest. Either of the latter two positions described above may be used, but the essential factor is that the direction of the pressure must be at right angles to the body surface at the level (as illustrated in Figure 5.3.8 -B).

[figure not shown]

Figure 5.3.8

Method:

The mobilizing is carried out by an oscillating pressure on the spinous processes, produced by the body and transmitted through the arms to the thumbs. It is important that this pressure is applied by the body weight over the hands and not by a squeezing action with the thumbs themselves.

According to the Maitland's concept of joint mobilization technique, Grade I will be provided to improve pain, Grade II mobilization will be provided to improve pain and Range of motion and Grade III mainly applied for mainly to improve range of motion. Therefore, according to the pain intensity of the patient therapist will decide the grades (Hengeveld & Banks, 2014).

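### The trial is labelled double-blind with participants blinded, but participants cannot be unaware of whether they exercise or receive manual therapy, so the self-rated pain and PSEQ outcomes are unblinded

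*Combined protocol and SAP*

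**What the plan says.** **Blinding claim.** Section 2.4 (Study Design) says: "This study is a Randomized Control Trial, Double- Blinded study. Participants and assessors will be blinded". It does not say what participants are blinded to.

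**The arms.** The same section describes an "experimental group which will receive thoracic mobility exercises" and a "control group which will receive myofascial release and joint mobilization treatment". Annex III (5.3) gives the delivery:

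- Exercise arm: three exercises done by the participant. "Subjects has to perform these exercise two times a day", for up to two weeks, with technique checked three times a week.
- Control arm, myofascial release: the participant lies prone and a therapist finds trigger points. "Constant pressure will be applied for 90 seconds to release the painful points".
- Control arm, Maitland mobilisation: "The mobilizing is carried out by an oscillating pressure on the spinous processes".

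**Allocation and assessors.** Section 2.8 says: "Participants will be allocated to one group by blindly select the number by lottery method". It adds that allocation was concealed and that assessors do not know the group.

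**Outcomes.** For pain, section 2.9 says: "Subjects will be asked to mark the number between 0 and 10 that fits best to their pain intensity". The PSEQ is a ten-item self-rating of confidence. Range of motion is measured by tape, and extensor strength is graded on the Oxford scale.

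**The concern.** Blinding participants to treatment requires that the two treatments cannot be told apart, usually through a sham or dummy in each arm. Here they differ in the most visible way possible: one is done by the participant, the other is done to the participant.

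This matters because of who produces the data. Pain is the subject of the general objective (1.2), and the participant rates it. For such an outcome the participant is the assessor, and staff blinding has no bearing on it. A participant who thinks they drew the better or the worse treatment may rate pain accordingly. Section 3 records that the investigators expect exercise to be more effective, and section 1.1 says that clinical practice already shows this, so there is an expectation that staff could pass on.

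The planned analysis (2.12) is a two-sample t test after the intervention, which cannot separate a difference in reporting from a difference in pain. A double-blind label would lead readers to discount a bias that the design does not prevent.

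**Working it through.** The plan gives no figure on this point, so there is none to reproduce. The check sets the blinding statement against the treatments, then against the outcome instruments.

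**Step 1. Can participants be unaware of their treatment?**

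| Feature | Exercise arm | Control arm | Source |
|---|---|---|---|
| Who acts | Participant | Therapist | 5.3 |
| What is done | Three active exercises, twice a day | Sustained pressure for 90 seconds, then oscillating mobilisation, lying prone | 5.3 |
| Sham or dummy of the other arm's treatment | None described | None described | 2.4, 5.3 |

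They cannot. Therapists cannot be blinded either, since they deliver the control treatment by hand.

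**Step 2. Do the other safeguards supply participant blinding?** Concealed allocation and the lottery draw (2.8) protect the assignment up to the moment it is made. They do not hide the treatment once it starts. Assessor blinding (2.8) covers only what the assessor rates.

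**Step 3. Which outcomes are exposed?** From the outcome list in 2.11 and the post-test form in 5.2.2:

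- Participant-rated: 8 VAS items (present pain, sitting, forward bending, standing, walking, sleeping, transferring, daily activities) + 1 overall PSEQ score = 9.
- Assessor-rated: 2 range-of-motion measures (flexion, extension) + 1 Oxford grade = 3.
- Total 9 + 3 = 12, so 9 of 12 are unblinded self-reports.

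**Step 4. How sensitive is the planned test to a reporting shift?** The documents give no size for such a shift, so this is an illustration over an assumed range and not an estimate for this trial. Suppose there is no true difference, n participants per arm, and a difference in reporting of b standard deviations between arms. The t statistic then follows a non-central t distribution with 2n − 2 degrees of freedom and non-centrality b√(n/2). For n = 30 (section 2.7) the degrees of freedom are 58 and √(30/2) = 3.87, so b = 0.2 gives a non-centrality of 0.77. For n = 21 (half of the 42 in section 2.6, before the dropout allowance) they are 40 and √(21/2) = 3.24. The chance that the two-sided 5% test rejects is:

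| Assumed shift b (SD) | 30 per arm | 21 per arm |
|---|---|---|
| 0 | 5.0% | 5.0% |
| 0.1 | 6.7% | 6.2% |
| 0.2 | 11.9% | 9.7% |
| 0.3 | 20.8% | 15.8% |
| 0.5 | 47.8% | 35.3% |

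The table shows only that the test treats a reporting shift as a treatment effect. The conclusion rests on steps 1 to 3.

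**The case against.** **Blinded may mean unaware of the hypothesis.** Both arms are active treatments, so participants could be kept from knowing which one the investigators favour. Section 2.4 does not exclude this, and the consent pages, where it might be explained, are not in the text reviewed. It stands as a possibility, but it would be partial masking and would not make 2.4 true as written. In addition, the headings of the pre-test and post-test questionnaires (5.2) name both treatments. If the forms are used as drafted, participants see the comparison where they rate their pain, though not an expected winner.

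**The count of 9 in 12 overstates the exposure.** Eight of the nine are ratings of one construct. By domain, the post-test form has four sections (pain, strength, range of motion, PSEQ), of which two are self-reported. That is a fair alternative count. Both are counts of measures, not sizes of bias, and on either one pain is exposed.

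**Strength and range of motion also depend on the participant's effort.** This is correct. Assessor blinding protects the grading and the reading of the tape, not the effort behind them. It limits how much protection can be claimed for the other three measures and does not help the self-reports.

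**No bias is shown, and relabelling removes none.** Also correct. Lack of participant blinding is inherent in comparing exercise with manual therapy, and such a comparison is legitimate. The fault lies in claiming a protection that is absent.

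**Conclusion.** The concern holds. Section 2.4 claims participant blinding that the treatments in 2.4 and Annex III make impossible, and nothing else in the plan supplies it. Nine of the 12 post-test measures, including every pain measure, are self-reports by participants who know their treatment. Three can be assessor-blinded. The direction and size of any expectation bias cannot be derived from the documents.

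The conclusion assumes only that no sham or dummy treatment is given, as is the case in the text available. A statement elsewhere that participants are kept unaware of the hypothesis would soften the point but not remove it. The trial remains worth doing with an accurate label. The correction should be made because it governs what the main pain result can claim.

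**What to change.** 1. In section 2.4, replace the double-blind statement with: assessor-blinded randomised trial; participants and therapists not blinded. If participants are to be kept unaware of the hypothesis, say so and state what they are told.
2. In sections 2.9 and 2.11, identify the VAS items and the PSEQ as unblinded self-reports. Limit the pain conclusion accordingly, naming expectation as an alternative explanation for any group difference.
3. In the participant information and on the questionnaires, present the two treatments neutrally, without calling either one experimental or the expected better treatment.
4. Ask participants not to reveal their treatment to the assessor who measures range of motion and strength.

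**Cost.** Wording in section 2.4, the outcome sections, the participant material and the conclusions, plus one instruction to participants. No added staff, visits or participants, and no change to either treatment. The downside is a less favourable design label. Section 2.13 runs the study from July 2022 to July 2024. If data collection is complete, items 3 and 4 can no longer be applied, but items 1 and 2 can still be made in the report.
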